Participants with assessment at time of seroconversion	n (%) ^a	X (X.X)	X (X.X)
Participants with assessment after seroconversion (on IP)	n (%) ^a	X (X.X)	X (X.X)
Participants with assessment after seroconversion (after IP)	n (%) ^a	X (X.X)	X (X.X)
Participants without assessment at time of seroconversion	n (%) ^a	X (X.X)	X (X.X)
Population-based sequencing			
Participants with assessment prior to seroconversion	n (%) ^a	X (X.X)	X (X.X)
Plasma HIV-1 RNA ≥2000 cop/mL	n (%) ^b	X (X.X)	X (X.X)
Plasma HIV-1 RNA <2000 cop/mL, ≥200 cop/mL	n (%) ^b	X (X.X)	X (X.X)
Participants with assessment at time of seroconversion	n (%) ^a	X (X.X)	X (X.X)
Plasma HIV-1 RNA ≥2000 cop/mL	n (%) ^b	X (X.X)	X (X.X)
Plasma HIV-1 RNA <2000 cop/mL, ≥200 cop/mL	n (%) ^b	X (X.X)	X (X.X)
Participants with assessment after seroconversion (on IP)	n (%) ^a	X (X.X)	X (X.X)
Plasma HIV-1 RNA ≥2000 cop/mL	n (%) ^b	X (X.X)	X (X.X)
Plasma HIV-1 RNA <2000 cop/mL, ≥200 cop/mL	n (%) ^b	X (X.X)	X (X.X)
Participants with assessment after seroconversion (after IP)	n (%) ^a	X (X.X)	X (X.X)
Plasma HIV-1 RNA ≥2000 cop/mL	n (%) ^b	X (X.X)	X (X.X)
Plasma HIV-1 RNA <2000 cop/mL, ≥200 cop/mL	n (%) ^b	X (X.X)	X (X.X)

HIV-1 = Human immunodeficiency virus type 1

Percentages are calculated out of the number of participants (per IPM 027 treatment) ^a In the virology population ^b With data ^c With a population-based sequencing assessment

Table 14.3.7.12
 Overview of HIV-1 RNA and Genotyping Information Availability
 Virology Population

Statistic	IPM 027 Dapivirine (N=XXX)	IPM 027 Placebo (N=XXX)	IPM 032 Overall (N=XXX)
Population-based sequencing			
Participants without assessment at time of seroconversion	n (%) ^a	X (X.X)	X (X.X)
HIV-1 Subtype			
A1	n (%) ^c	X (X.X)	X (X.X)
C	n (%) ^c	X (X.X)	X (X.X)
Etc.	n (%) ^c	X (X.X)	X (X.X)

HIV-1 = Human immunodeficiency virus type 1

Percentages are calculated out of the number of the number of participants (per IPM 027 treatment) ^a In the virology population ^b With ^c With a population-based sequencing assessment

Table 14.3.7.13.1
Summary of Mutational Patterns of Resistance-Associated Mutations at Seroconversion Timepoint
Virology Population

Subgroup: All IPM 032 participants		Statistic	IPM 027 Dapivirine (N=XXX)	IPM 027 Placebo (N=XXX)	IPM 032 Overall (N=XXX)
Resistance-Associated Mutation Combination					
Number of successful assessments	n (%) ^a		X (X.X)	X (X.X)	X (X.X)
NNRTI mutations					
None	n (%) ^a		X (X.X)	X (X.X)	X (X.X)

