6.3. Next Generation Sequencing

For NGS, the wild-type subtype B sequence, HXB2 (accession number K03455-1), will be used as reference. In the region sequenced, the only difference from the Stanford HIVdb consensus subtype B sequence is at codon 122 (HXB2: K122; Stanford: E122, respectively); K122 (or E122K) and E122 (or K122E) will be considered to be polymorphisms not related to NNRTI resistance in the analysis. The sensitivity for each NGS determination indicates the required prevalence for changes from the reference sequence to be detectable in the sample. The prevalences required are determined based on the statistical consideration of requiring at least 298 UMI for sensitivity to detect a 1.0% minority, 58 UMI for a 5.0% minority and 28 UMI for a 10.0% minority and will be summarized in tabulations. Samples with results showing less than 298, 58 or 28 UMI will be censored from each analysis performed to sensitivities to detect 1.0%, 5.0%, and 10.0% minority species, respectively.

^a These mutations do not have a resistance score when present alone; V179T with Y181C and M184I with K101E contribute to the score as a combination.

Frequency tabulations per minimum detectable prevalence (1.0%, 5.0%, 10.0%), as well as any additional NNRTI RAMs observed when results indicate UMI < 28, will be presented showing the percentage of participants with an amino acid change from reference at each position of the sequenced RT region.

All NGS results will be listed relative to the reference virus' amino acid sequence together with percent prevalence in the sample.

Frequency tabulations will be created per sensitivity cut-off (1.0%, 5.0%, 10.0%) for:

- The number (and percentage) of participants who had a resistance test performed.
- The number (and percentage) of participants with each individual NNRTI RAM.
- The number (and percentage) of participants with 0, 1, 2 or ≥ 3 mutations by class (NNRTI).
- The number (and percentage) of participants with combinations of specified NNRTI RAMs.

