Seroconversion Samples with Phenotypic Susceptibility Analysis Attempted, n (%) (b)	xx (x.x%)
HIV-1 seroconversion participants with any successful Phenotypic analysis (%) (b, e)	xx (x.x%)
Invalid or No Test Result, n (%) (b)	xx (x.x%)
Failed Testing (All phenotypes), n (%) (b)	xx (x.x%)
No test (Insufficient sample volume), n (%) (b,f)	xx (x.x%)

The percentage calculation is based on the total number of participants in the denoted section.

(a) Denominator = N1. (b) Denominator = N2. (c) Denominator = N3.

(d) Due to low UMI (< 28), these are considered to provide invalid results. Mutations detected in these samples will be reported separately.

(e) In the unlikely event of one to four of the five phenotypic test results for successful analysis being missing, this should be footnoted with the affected participant identifier.

(f) Some samples may have had inadequate volume to perform both the NGS and the phenotypic tests and so analysis was performed with NGS as priority, followed by phenotype determination.

Table 14.3.9.2.1
Summary of Numbers of Participants with an Amino Acid Change from Reference per Residue in the NGS Sequenced RT Region Among HIV-1 Seroconverters using Next Generation Sequencing with Paired Population-Based Genotyping Virology Population

Next Generation Sequencing: Number of Participants with an Amino Acid Change from Reference per Residue in the RT Region Among HIV-1 Seroconverters

		Statistic
Sensitivity Level 1%		
Participants with a Next Generation Sequencing Assessment (1% sensitivity: UMI \geq 298) at seroconversion time point (N)		XX
Amino Acid Change in RT (a)	NGS n (%)	Paired Population-based Genotype n (%)
Y82X	X (XX.X%)	X (XX.X%)
Y87X	X (XX.X%)	X (XX.X%)
Y88X	X (XX.X%)	X (XX.X%)
Y88X + Y88Z or Y88X/Z	X (XX.X%)	X (XX.X%)
Y90X	X (XX.X%)	X (XX.X%)
etc.		
Sensitivity Level 5%		
Participants with a Next Generation Sequencing Assessment (5% sensitivity: UMI \geq 58) at seroconversion time point (N)		XX
Amino Acid Change in RT (a)	NGS n (%)	Paired Population-based Genotype n (%)
Y82X	X (XX.X%)	X (XX.X%)
Y87X	X (XX.X%)	X (XX.X%)
Y88X	X (XX.X%)	X (XX.X%)

Y88X + Y88Z or Y88X/Z
Y90X
etc.

X (XX.X%) X (XX.X%)
X (XX.X%) X (XX.X%)

Sensitivity Level 10%

Participants with a Next Generation Sequencing Assessment (10% sensitivity: UMI ≥ 28) at seroconversion time point (N)

XX

Amino Acid Change in RT (a)

Y82X

Y87X

Y88X

Y88X + Y88Z or Y88X/Z

Y90X

etc.

Genotype	n (%)
X (XX.X%)	X (XX.X%)

Sensitivity Level > 10%

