Participants with a Next Generation Sequencing Assessment (> 10% sensitivity: UMI < 28) at seroconversion time point (N).

xx

Amino Acid Change in RT (a)

- Y82X
- Y87X
- Y88X
- Y88Z
- Y88X + Y88Z or Y88X/Z
- Y90X

etc.

N = Number of participants with data; n = number of participants with that observation.

NGS analyses should be considered exploratory.

The percentage calculation is based on the total number of participants with a next-generation sequencing assessment.

The sequenced region contains RT amino acids 80 – 150 and 152 - 212.

Participants may be counted more than once.

The reference sequence was the HXB2 sequence (NCBI accession number K03455.1, <https://www.ncbi.nlm.nih.gov/nuccore/1906382> accessed 13th January 2021). Within the NGS sequencing range, this differs from the Stanford consensus B sequence only at residue 122 (consensus amino acid: lysine, 'K'; HXB2: glutamic acid, 'E').

(a) Mixtures of variants with wild-type and mutant viral species (e.g. K103N at \leq 99% prevalence) for NGS data will be counted as the mutation being present (i.e. as 'K103N'). Similar mixtures detected using population-based genotyping (e.g. K103K/N) should be reported and counted as such. For NGS data, each mutant viral species will be counted (e.g. K103N and K103S from the same sample are counted in separate rows). Population-based genotypes having mixtures of mutations (e.g. K103N/S), will be reported as such and counted only once. Codons will be counted separately, therefore one participant with multiple mutations (e.g. K103N, E138A) will be counted more than once (i.e. twice in the example given).

[Note to programmer: Amino acids are listed in numeric order; population-based genotyping data is included as numbers are different from main analysis; residues with only null entries should be omitted; more than one variant at any residue should be reported separately; mixtures in the population-based genotypes should be counted if the mutation is present in the mixture (e.g. V108V/I would be counted with V108I in the NGS row). A separate line showing the mixture in the population-based genotype column only should then be included – mixtures will not be present by NGS. See above for Sensitivity > 10%]

Table 14.3.9.2.2
Summary of Numbers and Combinations of HIV-1 NNRTI Resistance-associated Mutations Among HIV-1 Seroconverters using Next Generation Sequencing with Paired Population-Based Genotyping Virology Population

		Statistic
Sensitivity Level 1%		

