N = Number of participants with data; n = number of participants with that observation; N/A = not applicable (mutations pattern was not detected); NNRTI = Non-nucleoside Reverse Transcriptase Inhibitor.

The percentage calculation is based on the total number of participants in the Virology Population and with a qualifying NGS assessment.

Participants are counted only once for each analysis (i.e. number of NNRTI RAMs per participant and number of each NNRTI RAM combination) within each sensitivity level.

The sequenced region contains RT amino acids 80 – 150 and 152 - 212. NGS analyses should be considered exploratory.

The Stanford HIV-1 Drug Resistance Database version 8.4 (dated 2017-06-16) was used.

(a) Mixtures of variants with wild-type and mutant viral minority species (e.g. K103N at \leq 99% prevalence for NGS data or K103K/N for population-based genotyping) will be counted as the mutation being present (i.e. as 'K103N' in this example). Each sequence will be counted only once.

(b) Mixtures observed using population-based genotyping will be reported as 'E138A/K', whereas these will be reported separately as 'E138A' and 'E138K' using NGS.

[Note to programmer: Amino acids are listed in numeric order; population-based genotyping included as numbers might be different from main analysis. To simplify the analysis of population-based genotype mixtures, include the count if the mixture includes a variant from the NGS analysis. Also, if there is more than one variant detected by NGS, these should be included in the listed row. The example: K101E + E138A + E138K + Y181C might be represented in the population-based genotype as K101E + E138A/K + Y181C the E138A + E138K would count as one mutation, but subsequently broken down by sequence. The example shows all possible population-based genotypes, only ones that apply should be included.]

Table 14.3.9.3.1
Summary of Phenotypic Susceptibility to Dapivirine and Other NNRTIs by Population-based Genotype
Virology Population

All Viruses	Dapivirine	Efavirenz	Etravirine	Nevirapine	Rilpivirine
N	XX	XX	XX	XX	XX
IC₅₀ (nM)					
Geometric mean (SD)	x.xx (x.xxx)				
(25th/median/75th)	(x.xx/x.xx/x.xx)	(x.xx/x.xx/x.xx)	(x.xx/x.xx/x.xx)	(x.xx/x.xx/x.xx)	(x.xx/x.xx/x.xx)
(Min,max)	(x.xx/xx.xx)	(x.xx/xx.xx)	(x.xx/xx.xx)	(x.xx/xx.xx)	(x.xx/xx.xx)
Fold change (a)					
Geometric mean (SD)	x.xx (x.xxx)				
(25th/median/75th)	(x.xx/x.xx/x.xx)	(x.xx/x.xx/x.xx)	(x.xx/x.xx/x.xx)	(x.xx/x.xx/x.xx)	(x.xx/x.xx/x.xx)

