(25th/median/75th)	(x.xx/x.xx/x.xx)	(x.xx/x.xx/x.xx)	(x.xx/x.xx/x.xx)	(x.xx/x.xx/x.xx)	(x.xx/x.xx/x.xx)
(Min,max)	(x.xx/xx.xx)	(x.xx/xx.xx)	(x.xx/xx.xx)	(x.xx/xx.xx)	(x.xx/xx.xx)
Viruses with A98G					
etc.					
Viruses with K101E					
etc.					
Viruses with K101E + E138A					
etc.					

(a) Fold change = IC₅₀/IC₅₀wild-type reference control.

(b) Mutations are included from population-based genotyping results (minority species mutations are less likely to influence phenotypes).

Table 14.3.9.4.1
Summary of Number of Participants with an Amino Acid Change from Reference per Residue in the RT Region Among HIV-1 Seroconversions
using Population-Based Genotyping (All Seroconversion ± 14-Days Data)
Virology Population

	Population-based Genotype n (%)
Participants with a population-based genotyping assessment at seroconversion time point (N)	XX
Stanford Number of NNRTI RAMs per participant (a)	
None	XX (X.X%)
Any	X (X.X%)
One	X (X.X%)
Two	X (X.X%)
Three or more	X (X.X%)
Average	0.XX
Stanford NNRTI resistance mutation combinations (b)	
A98G	X (X.X%)
K101E	X (X.X%)
K101E + E138A	X (X.X%)
K101E + E138A/K + Y181C	X (X.X%)
etc.	

N = Number of participants with data; n = number of participants with that observation; NNRTI = Non-nucleoside Reverse Transcriptase Inhibitor.

The percentage calculation is based on the total number of participants with a successful population-based genotyping assessment at seroconversion.

The Stanford HIV-1 Drug Resistance Database version 8.4 (dated 2017-06-16) was used.

(a) Instances of mixtures among the population-based genotypes that include one or more NNRTI RAM, are counted as if the mutation with the greatest drug resistance score was present.

LISTING SHELLS

Listing	Title
16.2.8.20	Next Generation Sequencing and Phenotype Susceptibility Data
16.2.8.20.1	Next Generation Sequencing: Listing of All Available Data
16.2.8.20.2	Next Generation Sequencing: Listing of Detected NNRTI Resistance-associated Mutations
16.2.8.20.4	Phenotypic Data: Listing of All Available Data
16.2.8.20.5	Genotypic Interpretations with Phenotypic Data: Full Listing for HIV-1 Seroconverters

Note: Population-based genotyping data are listed in the IPM 032 CSR Listings.

Listing 16.2.8.20.1
Next Generation Sequencing: Listing of All Available Data
Safety Population

PID (a)	Sample Date	Days (b)	Days (c)	Visit Day (d)	Log ₁₀ HIV-1 RNA (copies/mL)	Number UMI with Consensus	Sample Sensitivity (%)	Valid Result	Amino acid (% UMI) Change from Reference (e)

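### Paired sequencing tables base the population-genotype percentages on women with an NGS result, whether or not they have a population genotype

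*SAP*

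**What the plan says.** The addendum attempts NGS on every available seroconversion sample from the virology population (section 4.3). Its two side-by-side summaries with population sequencing are Tables 14.3.9.2.1 (changes by residue) and 14.3.9.2.2 (number and combinations of NNRTI mutations).

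- In both shells each sensitivity panel opens with one N, labelled "Participants with a Next Generation Sequencing Assessment" and followed by that panel's UMI condition. The population column has no N of its own and there is no row for women not genotyped.
- Footnote to 14.3.9.2.1: "The percentage calculation is based on the total number of participants with a next-generation sequencing assessment".
- Footnote to 14.3.9.2.2: "The percentage calculation is based on the total number of participants in the Virology Population and with a qualifying NGS assessment".
- The population column carries a percentage as well as a count. In 14.3.9.2.1 it is headed "Paired Population-based Genotype n" (%). The word 'paired' is in both table titles but is nowhere defined.
- Table 14.3.9.4.1, which shows population genotyping alone, has a different footnote: "The percentage calculation is based on the total number of participants with a successful population-based genotyping assessment at seroconversion".
- Under population-based sequencing, main SAP Table 14.3.7.12 has a row for "Participants without assessment at time of seroconversion".

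**The concern.** Relating NGS findings to population genotypes is one of the listed aims of the addendum (section 2), and section 6.2 plans a consistency check between the methods. A comparison of two assays needs both columns to rest on women who could have been positive by either. Here the denominator is conditioned on one assay only. A missing population genotype then lowers the population percentage in the same way as a negative one would, and the reader may take the gap for extra sensitivity of NGS. The addendum itself says that numbers are small (section 4.2), so one or two women can move a percentage visibly. The accountability table (14.3.9.1.1) counts NGS and phenotype results but not population genotypes, so it does not show the overlap.

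**Working it through.** The plan states no figure for this point, so there is none to reproduce. The check is a reading of the shells followed by denominator arithmetic.

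**Definitions, for one panel**
- N = women with a qualifying NGS result (panel N row and footnotes).
- m = those of the N who also have a successful population genotype.
- x = those of the m with a given mutation by population genotype.

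**Formula**
- Percentage as planned: x/N.
- Percentage among women tested by that method: x/m.
- Since x/N = (x/m) × (m/N), the planned percentage is the tested-women percentage multiplied by m/N. The NGS percentage is not affected. The factor cannot exceed 1, so the population column can be lowered but never raised.

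**Can m be smaller than N?** The documents allow for it. Table 14.3.7.12 has the row quoted above, main SAP section 9.3.2 plans to tabulate reasons why a resistance test was not done, and Listing 16.2.8.9 has a code for a genotype that was analysed without success. They do not say how many such women there are.

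**Range under assumed values.** Suppose each method finds a mutation in 20% of the women it tests. NGS prints 20%. The population column prints 20% × m/N:

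| N | 0 missing | 1 missing | 2 missing | 4 missing | 6 missing |
|---|---|---|---|---|---|
| 15 | 20.0% | 18.7% | 17.3% | 14.7% | 12.0% |
| 20 | 20.0% | 19.0% | 18.0% | 16.0% | 14.0% |
| 30 | 20.0% | 19.3% | 18.7% | 17.3% | 16.0% |

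**Whole-number example (assumed).** N = 20 and m = 16. Both methods find a mutation in the same 4 of the 16, and NGS finds 1 more among the 4 women not genotyped.
- As planned: NGS 5/20 = 25%, population 4/20 = 20%.
- Among the 16 with both results: 4/16 = 25% by each method.
- The 5-point gap comes entirely from a woman the population method never tested.

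**'None' and 'Average' in 14.3.9.2.2.** The shell does not say where an ungenotyped woman goes. In the example 'None' is 12/20 = 60% if she is left out, so that 'None' and 'Any' sum to 80%, or 16/20 = 80% if she is placed in it. The population 'Average' is undefined for the same reason.

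**The case against.** The strongest reply is that 'paired' already means both results. The programmer note to 14.3.9.2.1 says the population data are repeated because the numbers differ from the main analysis, which shows a deliberate restriction to the NGS subset. That restriction runs one way only: it limits the population data to women with NGS, and nothing limits the tables to women with a population genotype. If full pairing was intended, the N rows and footnotes do not say so and still need changing.

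It can also be said that main SAP 9.3.2 plans genotyping for all seroconverters, that the Table 14.3.7.12 row may hold zero, and that population results had already been reported in the April 2020 study report. This stands as a limit on size: the effect may be nil. Other outputs also help. The tables print counts, section 4.4 promises numbers of missing analyses, and Listing 16.2.8.20.5 in the shells shows the mutations by each method woman by woman. These let a careful reader trace the gap, but they do not correct the printed percentages.

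Four stronger readings are tempting and are not supported.

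- A reader might infer from the missing word 'qualifying' in the 14.3.9.2.1 footnote that samples below the UMI threshold stay in a panel's denominator. They do not: each panel prints its own UMI-specific N, and section 6.3 says such samples "will be censored from each analysis performed to sensitivities to detect 1.0%, 5.0%, and 10.0% minority species".
- A reader might take Table 14.3.9.4.1 as the same data with a better denominator. It covers all seroconversion genotypes, not the NGS subset, so its N should differ. It shows only that the plan conditions on a successful genotype when that method stands alone.
- A reader might expect one mutation to carry the same percentage in both paired tables. They count differently by design: 14.3.9.2.1 by residue, with a woman possibly counted more than once, and 14.3.9.2.2 by combination, once per woman.
- A reader might conclude that ungenotyped women are tabulated as mutation-free. The shell does not place them in 'None'. What is established is that they dilute the mutation and 'Any' rows.

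**Conclusion.** The point holds in this form: as written, the footnotes and panel N of both paired tables put women without a population genotype into the population column's denominator, and its mutation and 'Any' percentages shrink by m/N. The distortion is one-sided, in the direction of making NGS look more sensitive. It rests on at least one woman having a qualifying NGS result and no successful population genotype at seroconversion. The documents foresee this but do not count it, so the size is unknown and is zero under complete overlap. The analysis is supplementary, descriptive and labelled exploratory; no test, error rate or decision rule is touched. It is worth correcting because the affected tables are the summary comparison the addendum sets out to make.

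**What to change.** In each panel of both tables, base both columns of the comparison on women who have a qualifying NGS result for that panel and a successful population genotype at seroconversion (± 14 days), and print that N. Show women with NGS only in a separate NGS-only column. An acceptable alternative is to give the population column its own N and add a 'not genotyped' row. Either way, define 'paired' in a footnote and state how 'None' and 'Average' treat women without a genotype.

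The cost is two footnotes and the denominator code, plus a possibly smaller N in the paired columns. No new data are needed.

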To confirm to us that you can access this information electronically, which will be similar to other electronic notices and disclosures that we will provide to you, please verify that you were able to read this electronic disclosure and that you also were able to print on paper or electronically save this page for your future reference and access or that you were able to e-mail this disclosure and consent to an address where you will be able to print on paper or save it for your future reference and access. Further, if you consent to receiving notices and disclosures exclusively in electronic format on the terms and conditions described above, please let us know by clicking the 'I agree' button below.

By checking the 'I agree' box, I confirm that:

- I can access and read this Electronic CONSENT TO ELECTRONIC RECEIPT OF ELECTRONIC CONSUMER DISCLOSURES document; and
- I can print on paper the disclosure or save or send the disclosure to a place where I can print it, for future reference and access; and
- Until or unless I notify International Partnership For Microbicides, Inc. as described above, I consent to receive from exclusively through electronic means all notices, disclosures, authorizations, acknowledgements, and other documents that are required to be provided or made available to me by International Partnership For Microbicides, Inc. during the course of my relationship with you.

IPM 032 VIROLOGY ADDENDUM SAP

APPENDIX 1

TABLE AND LISTING SHELLS – VERSION 1.0, 24 MAY 2021

TABLE SHELLS

Table	Title
14.3.9	Next Generation Sequencing (NGS) and Phenotypic Susceptibility Analysis
14.3.9.1	Accountability
14.3.9.1.1	Sample Availability
14.3.9.2	Summary of NGS and Paired Population-based Genotype Analysis
14.3.9.2.1	Summary of Number of Participants with an Amino Acid Change from Reference per Residue in the NGS Sequenced RT Region Among HIV-1 Seroconversions using Next Generation Sequencing with Paired Population-Based Genotypes
14.3.9.2.2	Summary of Numbers and Combinations of HIV-1 NNRTI Resistance-associated Mutations Among HIV-1 Seroconverters using Next Generation Sequencing with Paired Population-Based Genotypes
14.3.9.3	Phenotypic Susceptibility Analysis
14.3.9.3.1	Summary of Phenotypic Susceptibility to Dapivirine and Other NNRTIs by Population-based Genotype
14.3.9.4	Summary of All Seroconversion Population-Based Genotyping
14.3.9.4.1	Summary of Number of Participants with an Amino Acid Change from Reference per Residue in the RT Region Among HIV-1 Seroconversions using Population-Based Genotyping (All Seroconversion Data)

Table 14.3.9.1.1
Sample Availability
Virology Population

	Statistic
HIV-1 Seroconversion Participants, N1	XX
Seroconversion Samples Available, N2 (%) (a)	xx (x.x%)
No sample n (%) (a)	xx (x.x%)
Sample not suitable n (%) (a)	xx (x.x%)
No consent n (%) (a)	xx (x.x%)
Seroconversion Samples with NGS Analysis Attempted, n (%) (b)	xx (x.x%)
HIV-1 seroconversion participants with a successful NGS genotype, N3 (%) (b)	xx (x.x%)
Sensitivity to detect RAMs present with at least:	
≤ 1% variant, n (%) (c)	xx (x.x%)
> 1% to 5% variant, n (%) (c)	xx (x.x%)
> 5% to 10% variant, n (%) (c)	xx (x.x%)
Invalid Result, n (%) (b, d)	xx (x.x%)
Test performed, no output (c)	xx (x.x%)
Sensitivity to detect RAMs present at:	
>10% to 20% variant, n (%) (c,d)	xx (x.x%)
> 20% variant, n (%) (c,d)	xx (x.x%)
Seroconversion Samples with Phenotypic Susceptibility Analysis Attempted, n (%) (b)	xx (x.x%)
HIV-1 seroconversion participants with any successful Phenotypic analysis (%) (b, e)	xx (x.x%)
Invalid or No Test Result, n (%) (b)	xx (x.x%)
Failed Testing (All phenotypes), n (%) (b)	xx (x.x%)
No test (Insufficient sample volume), n (%) (b,f)	xx (x.x%)

The percentage calculation is based on the total number of participants in the denoted section.

(a) Denominator = N1. (b) Denominator = N2. (c) Denominator = N3.

(d) Due to low UMI (< 28), these are considered to provide invalid results. Mutations detected in these samples will be reported separately.

(e) In the unlikely event of one to four of the five phenotypic test results for successful analysis being missing, this should be footnoted with the affected participant identifier.

(f) Some samples may have had inadequate volume to perform both the NGS and the phenotypic tests and so analysis was performed with NGS as priority, followed by phenotype determination.

Table 14.3.9.2.1
Summary of Numbers of Participants with an Amino Acid Change from Reference per Residue in the NGS Sequenced RT Region Among HIV-1 Seroconverters using Next Generation Sequencing with Paired Population-Based Genotyping Virology Population

Next Generation Sequencing: Number of Participants with an Amino Acid Change from Reference per Residue in the RT Region Among HIV-1 Seroconverters

		Statistic
Sensitivity Level 1%		
Participants with a Next Generation Sequencing Assessment (1% sensitivity: UMI \geq 298) at seroconversion time point (N)		XX
Amino Acid Change in RT (a)	NGS n (%)	Paired Population-based Genotype n (%)
Y82X	X (XX.X%)	X (XX.X%)
Y87X	X (XX.X%)	X (XX.X%)
Y88X	X (XX.X%)	X (XX.X%)
Y88X + Y88Z or Y88X/Z	X (XX.X%)	X (XX.X%)
Y90X	X (XX.X%)	X (XX.X%)
etc.		
Sensitivity Level 5%		
Participants with a Next Generation Sequencing Assessment (5% sensitivity: UMI \geq 58) at seroconversion time point (N)		XX
Amino Acid Change in RT (a)	NGS n (%)	Paired Population-based Genotype n (%)
Y82X	X (XX.X%)	X (XX.X%)
Y87X	X (XX.X%)	X (XX.X%)
Y88X	X (XX.X%)	X (XX.X%)

Y88X + Y88Z or Y88X/Z
Y90X
etc.

X (XX.X%) X (XX.X%)
X (XX.X%) X (XX.X%)

Sensitivity Level 10%

Participants with a Next Generation Sequencing Assessment (10% sensitivity: UMI ≥ 28) at seroconversion time point (N)

XX

Amino Acid Change in RT (a)

Y82X

Y87X

Y88X

Y88X + Y88Z or Y88X/Z

Y90X

etc.

NGS n (%)	Genotype n (%)
X (XX.X%)	X (XX.X%)

Sensitivity Level > 10%

Participants with a Next Generation Sequencing Assessment (> 10% sensitivity: UMI < 28) at seroconversion time point (N).

xx

Amino Acid Change in RT (a)

- Y82X
- Y87X
- Y88X
- Y88Z
- Y88X + Y88Z or Y88X/Z
- Y90X

etc.

N = Number of participants with data; n = number of participants with that observation.

NGS analyses should be considered exploratory.

The percentage calculation is based on the total number of participants with a next-generation sequencing assessment.

The sequenced region contains RT amino acids 80 – 150 and 152 - 212.

Participants may be counted more than once.

The reference sequence was the HXB2 sequence (NCBI accession number K03455.1, <https://www.ncbi.nlm.nih.gov/nuccore/1906382> accessed 13th January 2021). Within the NGS sequencing range, this differs from the Stanford consensus B sequence only at residue 122 (consensus amino acid: lysine, 'K'; HXB2: glutamic acid, 'E').

(a) Mixtures of variants with wild-type and mutant viral species (e.g. K103N at \leq 99% prevalence) for NGS data will be counted as the mutation being present (i.e. as 'K103N'). Similar mixtures detected using population-based genotyping (e.g. K103K/N) should be reported and counted as such. For NGS data, each mutant viral species will be counted (e.g. K103N and K103S from the same sample are counted in separate rows). Population-based genotypes having mixtures of mutations (e.g. K103N/S), will be reported as such and counted only once. Codons will be counted separately, therefore one participant with multiple mutations (e.g. K103N, E138A) will be counted more than once (i.e. twice in the example given).

[Note to programmer: Amino acids are listed in numeric order; population-based genotyping data is included as numbers are different from main analysis; residues with only null entries should be omitted; more than one variant at any residue should be reported separately; mixtures in the population-based genotypes should be counted if the mutation is present in the mixture (e.g. V108V/I would be counted with V108I in the NGS row). A separate line showing the mixture in the population-based genotype column only should then be included – mixtures will not be present by NGS. See above for Sensitivity > 10%]

Table 14.3.9.2.2
Summary of Numbers and Combinations of HIV-1 NNRTI Resistance-associated Mutations Among HIV-1 Seroconverters using Next Generation Sequencing with Paired Population-Based Genotyping Virology Population

		Statistic
Sensitivity Level 1%		
Participants with a Next Generation Sequencing Assessment (1% sensitivity: UMI \geq 298) at seroconversion time point (N)		XX
Stanford Number of NNRTI RAMs per participant (a)	NGS n (%)	Population-based Genotype n (%)
None	XX (X.X%)	XX (X.X%)
Any	X (X.X%)	X (X.X%)
One	X (X.X%)	X (X.X%)
Two	X (X.X%)	X (X.X%)
Three or more	X (X.X%)	X (X.X%)
Average	0.XX	0.XX
Stanford NNRTI resistance mutation combinations (a)		
A98G	X (X.X%)	X (X.X%)
K101E	X (X.X%)	X (X.X%)
K101E + E138A	X (X.X%)	X (X.X%)
K101E + E138A + E138K (or K101E + E138A/K (b))	X (X.X%)	X (X.X%)
etc.		
Sensitivity Level 5%		
Participants with a Next Generation Sequencing Assessment (5% sensitivity: UMI \geq 58) at seroconversion time point (N)		XX

	NGS n (%)	Population-based Genotype n (%)
Stanford Number of NNRTI RAMs per participant (a)		
None	XX (X.X%)	XX (X.X%)
Any	X (X.X%)	X (X.X%)
One	X (X.X%)	X (X.X%)
Two	X (X.X%)	X (X.X%)
Three or more	X (X.X%)	X (X.X%)
Average	0.XX	0.XX
 Stanford NNRTI resistance mutation combinations (a)		
A98G	X (X.X%)	X (X.X%)
K101E	X (X.X%)	X (X.X%)
K101E + E138A	X (X.X%)	X (X.X%)
K101E + E138A + E138K (or K101E + E138A/K (b))	X (X.X%)	X (X.X%)
etc.		

Sensitivity Level 10%

Participants with a Next Generation Sequencing Assessment (10% sensitivity: UMI ≥ 28) at seroconversion time point (N)

XX

	NGS n (%)	Population-based Genotype n (%)
Stanford Number of NNRTI RAMs per participant (a)		
None	XX (X.X%)	XX (X.X%)
Any	X (X.X%)	X (X.X%)
One	X (X.X%)	X (X.X%)
Two	X (X.X%)	X (X.X%)
Three or more	X (X.X%)	X (X.X%)
Average	0.XX	0.XX
Stanford NNRTI resistance mutation combinations (a)		
A98G	X (X.X%)	X (X.X%)
K101E	X (X.X%)	X (X.X%)
K101E + E138A	X (X.X%)	X (X.X%)
K101E + E138A + E138K (or K101E + E138A/K (b))	X (X.X%)	X (X.X%)
etc. as above		

Sensitivity Level > 10%

Participants with a Next Generation Sequencing Assessment (> 10% sensitivity: UMI < 28) at seroconversion time point (N)

XX

	NGS n (%)	Population-based Genotype n (%)
Stanford Number of NNRTI RAMs per participant (a)		
None	XX (X.X%)	XX (X.X%)
Any	X (X.X%)	X (X.X%)
One	X (X.X%)	X (X.X%)
Two	X (X.X%)	X (X.X%)
Three or more	X (X.X%)	X (X.X%)
Average	0.XX	0.XX
Stanford NNRTI RAM combinations (a)		
A98G	X (X.X%)	X (X.X%)
K101E	X (X.X%)	X (X.X%)
K101E + E138A	X (X.X%)	X (X.X%)
K101E + E138A + E138K (or K101E + E138A/K (b))	X (X.X%)	X (X.X%)
etc. as above		

N = Number of participants with data; n = number of participants with that observation; N/A = not applicable (mutations pattern was not detected); NNRTI = Non-nucleoside Reverse Transcriptase Inhibitor.

The percentage calculation is based on the total number of participants in the Virology Population and with a qualifying NGS assessment.

Participants are counted only once for each analysis (i.e. number of NNRTI RAMs per participant and number of each NNRTI RAM combination) within each sensitivity level.

The sequenced region contains RT amino acids 80 – 150 and 152 - 212. NGS analyses should be considered exploratory.

The Stanford HIV-1 Drug Resistance Database version 8.4 (dated 2017-06-16) was used.

(a) Mixtures of variants with wild-type and mutant viral minority species (e.g. K103N at \leq 99% prevalence for NGS data or K103K/N for population-based genotyping) will be counted as the mutation being present (i.e. as 'K103N' in this example). Each sequence will be counted only once.

(b) Mixtures observed using population-based genotyping will be reported as 'E138A/K', whereas these will be reported separately as 'E138A' and 'E138K' using NGS.

[Note to programmer: Amino acids are listed in numeric order; population-based genotyping included as numbers might be different from main analysis. To simplify the analysis of population-based genotype mixtures, include the count if the mixture includes a variant from the NGS analysis. Also, if there is more than one variant detected by NGS, these should be included in the listed row. The example: K101E + E138A + E138K + Y181C might be represented in the population-based genotype as K101E + E138A/K + Y181C the E138A + E138K would count as one mutation, but subsequently broken down by sequence. The example shows all possible population-based genotypes, only ones that apply should be included.]

Table 14.3.9.3.1
Summary of Phenotypic Susceptibility to Dapivirine and Other NNRTIs by Population-based Genotype
Virology Population

All Viruses	Dapivirine	Efavirenz	Etravirine	Nevirapine	Rilpivirine
N	XX	XX	XX	XX	XX
IC₅₀ (nM)					
Geometric mean (SD)	x.xx (x.xxx)				
(25th/median/75th)	(x.xx/x.xx/x.xx)	(x.xx/x.xx/x.xx)	(x.xx/x.xx/x.xx)	(x.xx/x.xx/x.xx)	(x.xx/x.xx/x.xx)
(Min,max)	(x.xx/xx.xx)	(x.xx/xx.xx)	(x.xx/xx.xx)	(x.xx/xx.xx)	(x.xx/xx.xx)
Fold change (a)					
Geometric mean (SD)	x.xx (x.xxx)				
(25th/median/75th)	(x.xx/x.xx/x.xx)	(x.xx/x.xx/x.xx)	(x.xx/x.xx/x.xx)	(x.xx/x.xx/x.xx)	(x.xx/x.xx/x.xx)
(Min,max)	(x.xx/xx.xx)	(x.xx/xx.xx)	(x.xx/xx.xx)	(x.xx/xx.xx)	(x.xx/xx.xx)
Wild-type viruses (b)					
N	XX	XX	XX	XX	XX
IC₅₀ (nM)					
Geometric mean (SD)	x.xx (x.xxx)				
(25th/median/75th)	(x.xx/x.xx/x.xx)	(x.xx/x.xx/x.xx)	(x.xx/x.xx/x.xx)	(x.xx/x.xx/x.xx)	(x.xx/x.xx/x.xx)
(Min,max)	(x.xx/xx.xx)	(x.xx/xx.xx)	(x.xx/xx.xx)	(x.xx/xx.xx)	(x.xx/xx.xx)
Fold change (a)					
Geometric mean (SD)	x.xx (x.xxx)				
(25th/median/75th)	(x.xx/x.xx/x.xx)	(x.xx/x.xx/x.xx)	(x.xx/x.xx/x.xx)	(x.xx/x.xx/x.xx)	(x.xx/x.xx/x.xx)
(Min,max)	(x.xx/xx.xx)	(x.xx/xx.xx)	(x.xx/xx.xx)	(x.xx/xx.xx)	(x.xx/xx.xx)

Viruses with any NNRTI RAM

N	XX	XX	XX	XX	XX
IC₅₀ (nM)					
Geometric mean (SD)	x.xx (x.xxx)				
(25th/median/75th)	(x.xx/x.xx/x.xx)	(x.xx/x.xx/x.xx)	(x.xx/x.xx/x.xx)	(x.xx/x.xx/x.xx)	(x.xx/x.xx/x.xx)
(Min,max)	(x.xx/xx.xx)	(x.xx/xx.xx)	(x.xx/xx.xx)	(x.xx/xx.xx)	(x.xx/xx.xx)
Fold change (a)					
Geometric mean (SD)	x.xx (x.xxx)				
(25th/median/75th)	(x.xx/x.xx/x.xx)	(x.xx/x.xx/x.xx)	(x.xx/x.xx/x.xx)	(x.xx/x.xx/x.xx)	(x.xx/x.xx/x.xx)
(Min,max)	(x.xx/xx.xx)	(x.xx/xx.xx)	(x.xx/xx.xx)	(x.xx/xx.xx)	(x.xx/xx.xx)

Viruses with one NNRTI RAM

N	XX	XX	XX	XX	XX
IC₅₀ (nM)					
Geometric mean (SD)	x.xx (x.xxx)				
(25th/median/75th)	(x.xx/x.xx/x.xx)	(x.xx/x.xx/x.xx)	(x.xx/x.xx/x.xx)	(x.xx/x.xx/x.xx)	(x.xx/x.xx/x.xx)
(Min,max)	(x.xx/xx.xx)	(x.xx/xx.xx)	(x.xx/xx.xx)	(x.xx/xx.xx)	(x.xx/xx.xx)
Fold change (a)					
Geometric mean (SD)	x.xx (x.xxx)				
(25th/median/75th)	(x.xx/x.xx/x.xx)	(x.xx/x.xx/x.xx)	(x.xx/x.xx/x.xx)	(x.xx/x.xx/x.xx)	(x.xx/x.xx/x.xx)
(Min,max)	(x.xx/xx.xx)	(x.xx/xx.xx)	(x.xx/xx.xx)	(x.xx/xx.xx)	(x.xx/xx.xx)

Viruses with two NNRTI RAMs

N	XX	XX	XX	XX	XX
IC₅₀ (nM)					
Geometric mean (SD)	x.xx (x.xxx)				
(25th/median/75th)	(x.xx/x.xx/x.xx)	(x.xx/x.xx/x.xx)	(x.xx/x.xx/x.xx)	(x.xx/x.xx/x.xx)	(x.xx/x.xx/x.xx)

(Min,max)	(x.xx/xx.xx)	(x.xx/xx.xx)	(x.xx/xx.xx)	(x.xx/xx.xx)	(x.xx/xx.xx)
Fold change (a)					
Geometric mean (SD)	x.xx (x.xxxx)				
(25th/median/75th)	(x.xx/x.xx/x.xx)	(x.xx/x.xx/x.xx)	(x.xx/x.xx/x.xx)	(x.xx/x.xx/x.xx)	(x.xx/x.xx/x.xx)
(Min,max)	(x.xx/xx.xx)	(x.xx/xx.xx)	(x.xx/xx.xx)	(x.xx/xx.xx)	(x.xx/xx.xx)
Viruses with three or more NNRTI RAMs					
N	XX	XX	XX	XX	XX
IC₅₀ (nM)					
Geometric mean (SD)	x.xx (x.xxxx)				
(25th/median/75th)	(x.xx/x.xx/x.xx)	(x.xx/x.xx/x.xx)	(x.xx/x.xx/x.xx)	(x.xx/x.xx/x.xx)	(x.xx/x.xx/x.xx)
(Min,max)	(x.xx/xx.xx)	(x.xx/xx.xx)	(x.xx/xx.xx)	(x.xx/xx.xx)	(x.xx/xx.xx)
Fold change (a)					
Geometric mean (SD)	x.xx (x.xxxx)				
(25th/median/75th)	(x.xx/x.xx/x.xx)	(x.xx/x.xx/x.xx)	(x.xx/x.xx/x.xx)	(x.xx/x.xx/x.xx)	(x.xx/x.xx/x.xx)
(Min,max)	(x.xx/xx.xx)	(x.xx/xx.xx)	(x.xx/xx.xx)	(x.xx/xx.xx)	(x.xx/xx.xx)
Viruses with A98G					
etc.					
Viruses with K101E					
etc.					
Viruses with K101E + E138A					
etc.					

(a) Fold change = IC₅₀/IC₅₀wild-type reference control.

(b) Mutations are included from population-based genotyping results (minority species mutations are less likely to influence phenotypes).

Table 14.3.9.4.1
Summary of Number of Participants with an Amino Acid Change from Reference per Residue in the RT Region Among HIV-1 Seroconversions using Population-Based Genotyping (All Seroconversion ± 14-Days Data)
Virology Population

	Population-based Genotype n (%)
Participants with a population-based genotyping assessment at seroconversion time point (N)	XX
Stanford Number of NNRTI RAMs per participant (a)	
None	XX (X.X%)
Any	X (X.X%)
